**NCT 02837328**

**July 5th, 2018**

### *Statistical analysis*

The goal of the pilot study was to assess adherence to the Mg supplement, and feasibility of using the ZioPatch and collect preliminary data on PACs, a predictor of AF. The targeted sample size of 60 was determined to detect a difference in the change in log PACs (follow-up minus baseline) between treatment groups of 0.79 standard deviation units with 80% power and 5% type I error (2-sided), assuming 5 participants would not complete follow-up.

All analyses were intent-to-treat. Descriptive statistics are provided according to treatment assignment for baseline characteristics, adherence, Mg concentrations and other outcomes. Differences in baseline characteristics between groups were assessed using t-tests for continuous variables and Fisher's exact tests for categorical variables. Linear regression was used to evaluate whether change in outcomes differed according to treatment assignment, adjusting for the randomization stratification factor (age  $\geq 65$  vs  $< 65$ ) and baseline value of the outcome with robust variance estimates for confidence intervals and P-values. Post-hoc sensitivity analyses further adjusted for sex. As PAC burden is highly skewed, we pre-specified using log PAC burden for analysis and reported the ratio of geometric means. Pre-specified subgroup analyses were also performed, stratified by baseline magnesium concentration ( $<$  vs.  $\geq$  median). A 2-sided p-value of  $< 0.05$  was used to indicate statistical significance. Analyses were conducted using R [21] version 3.4.0 (R Foundation, Vienna, Austria).

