### *Study participants*

Participants 55 years of age or older were recruited using fliers, the University of Minnesota StudyFinder website, invitations to individuals enrolled in the ResearchMatch research volunteer database, and invitations to University of Minnesota School of Public Health employees.

Exclusion criteria included a prior history of heart disease (coronary heart disease, heart failure, AF), stroke, known kidney disease; use of type I or III antiarrhythmic drugs or digoxin; current use of magnesium supplements; any prior history of allergy or intolerance to magnesium; lactose intolerance; prior history of inflammatory bowel disease or any severe gastrointestinal disorder. Use of multivitamins was allowable, since these typically contain relatively low dosages of Mg (e.g. 50 mg).

Eligible participants attended a baseline visit where measurements were conducted and a Zio® XT Patch (ZioPatch; iRhythm Technologies, Inc., San Francisco, California) heart rhythm monitor was applied by trained staff. After wearing the ZioPatch for 2 weeks, participants were randomized 1:1 to either 400 mg magnesium oxide or placebo using block randomization within two strata of age (younger than 65 and 65 and older). The randomization was carried out separately for the two randomization strata, age younger than 65 and 65 and older. In each group, a randomization schedule was generated using randomly permuted blocks of random sizes.

Block sizes of 2, 4 or 6 were permitted. The randomization was implemented using the `blockrand` package in R.

Following randomization, participants were mailed the study intervention, which they took for a total of 12 weeks. Ten weeks after beginning the study intervention, participants took part in a follow-up clinic visit, and a second ZioPatch was applied. Participants continued the study intervention until the second ZioPatch was removed (2 weeks after the follow-up clinic visit) (Figure 1).

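### Does the intent-to-treat label fail because the change-score regression can only use participants with a follow-up recording?

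*SAP*

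**What the plan says.** The whole analysis plan is the SAP section Statistical analysis. It declares that "All analyses were intent-to-treat" and does not define the term. The model is given as "Linear regression was used to evaluate whether change in outcomes differed according to treatment assignment", "adjusting for the randomization stratification factor" (age 65 and over against under 65) and for the "baseline value of the outcome with robust variance estimates for confidence intervals and P-values". PAC burden is analysed on the log scale.

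The sample size of 60 targets a between-group difference of 0.79 SD in change in log PACs, with 80% power at a two-sided 5% level, "assuming 5 participants would not complete follow-up".

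The Protocol, Study participants, places the baseline recording before allocation: "After wearing the ZioPatch for 2 weeks, participants were randomized 1:1 to either 400 mg magnesium oxide or placebo". The second patch is applied at week 10 and worn for two weeks, and no PAC recording is planned in between. Neither document gives an imputation method, a missing-data assumption or a sensitivity analysis for missing outcomes. The only sensitivity analysis named is a post-hoc adjustment for sex.

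**The concern.** A change score needs both recordings. Anyone who misses the second patch drops out of the regression, so the estimate comes from randomised participants with follow-up, about 55 of 60 on the plan's own expectation. A strict reader of intent-to-treat expects every randomised person to be counted and would say that the label claims more than the model delivers.

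Tolerability makes this more pointed. The Protocol excludes people with prior magnesium intolerance or severe gastrointestinal disease, which suggests that side effects on the active capsule were foreseen. If losses clustered in the magnesium arm, and the people lost would have had a different PAC change, the comparison would be biased in a trial too small to absorb it, with no planned analysis to show how far.

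**Working it through.** **Inputs.** From the SAP: N = 60, difference 0.79 SD, power 80%, two-sided 5%, 5 non-completers, covariates age stratum and baseline value. From the Protocol: 1:1 allocation, so about 30 per arm, and one PAC recording after randomisation. The split of losses between arms, and how far the people lost differ from completers, are not in the documents and are assumed below.

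**1. The plan's own figure.** A two-sample t-test for 0.79 SD at 80% power needs 26.15 per arm, rounded up to 27. That gives 2 × 27 = 54 completers, and 54 + 5 = 59, against 60 stated. The figure reproduces to within one participant. With 55 analysed (28 + 27), power is 82.0%; with all 60 it would be 85.3%. The expected loss is already paid for, so this is not a power question.

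**2. Size of the loss.** Overall 5/60 = 8.3%. If every loss fell in one arm, 5/30 = 16.7% of that arm.

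**3. When the completer regression is biased.** The model contains arm, age stratum and baseline outcome. If it is correctly specified and dropout depends only on those variables, the regression among people with follow-up estimates the treatment difference without bias, even if dropout is higher on magnesium. A simulation with an assumed data model (30 per arm, no true effect, all 5 losses in the magnesium arm, 20,000 runs) gave a bias of 0.000 SD for losses at random within that arm and 0.001 SD for losses that depended on baseline PACs. Bias arises only when dropout is also related to the unseen follow-up value given those covariates.

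**4. Size of that bias under assumed extremes.** Suppose k of 30 magnesium participants are lost and their mean change differs from that of comparable completers by d SD. Then:

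- bias = (k/30) × d
- SE of the difference with 25 and 30 analysed = √(1/25 + 1/30) = 0.271 SD
- false-positive rate under no true effect, with z = bias/SE: P(Z > 1.96 − z) + P(Z < −1.96 − z)

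With k = 5, all losses in one arm:

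| d (assumed) | Bias, SD | Bias / SE | Share of 0.79 | False-positive rate |
|---|---|---|---|---|
| 0.5 | 0.083 | 0.31 | 11% | about 6% |
| 1.0 | 0.167 | 0.62 | 21% | about 9% |
| 1.5 | 0.250 | 0.92 | 32% | about 15% |

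With k = 3 on magnesium and no losses on placebo, d = 0.5 and 1.0 give 0.05 and 0.10 SD. With a 3:2 split and the same d in both arms, the net bias is (3/30 − 2/30) × d, which is 0.033 SD at d = 1.0.

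**5. What imputation would add.** Multiple imputation from arm, age stratum and baseline PACs conditions on what the regression already uses and also assumes missing at random. The only new predictors would be sex and the day-21 and day-42 online answers on compliance and adverse effects, used to fill about 5 values. People who leave may not have answered those questionnaires.

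**The case for a change.** The strongest case for a change is that an unqualified label for all analyses sits beside a model that cannot include the people the plan expects to lose. Nothing is said about why that is acceptable, and no analysis tests dropout related to outcome. The questionnaire answers before week 10 are already collected, and a delta-shift analysis would cost one short script.

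Part of this stands. The SAP leaves intent-to-treat undefined, is silent on missing outcomes, and has no check on dropout related to the unseen PAC change.

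The rest does not carry. The claim that the plan offers no protection is wrong, because the adjusted model handles dropout that depends on arm, age stratum and baseline. The tolerability argument is incomplete. The Protocol also excludes lactose intolerance, and the placebo is lactose, so the exclusions screen for tolerability on both sides. Screening out susceptible people should also make such dropout rarer. The 5 expected losses are not attributed to a cause or an arm. Stopping the capsules is not the same as missing the outcome: nothing in the Protocol withdraws people who stop from the second patch, and anyone who wears it stays in the analysis. Nor is any reason evident why leaving for gastrointestinal symptoms should go with a different PAC change.

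**Conclusion.** The concern does not hold as a defect in the plan. What remains is missing detail that an analyst fills in the usual way: analyse people as randomised among those with a follow-up recording, and show losses and reasons by arm in the participant flow. The planned regression already does the first, and the sample size already allows for the 5 losses.

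The residual risk is outcome-related dropout. A shift of 0.08 to 0.17 SD needs all 5 losses in one arm and a 0.5 to 1.0 SD difference from comparable completers. The 0.25 SD figure needs a difference of 1.5 SD, almost twice the effect the trial was sized to detect. With balanced losses and similar differences in both arms the shift is near zero. None of these dropout patterns comes from the documents.

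Making multiple imputation the main analysis would swap one missing-at-random analysis for another with little gain. A delta-shift analysis is the only addition that addresses the remaining question. It is optional in a pilot aimed at adherence, feasibility and preliminary PAC data, and it would correct no wrong result. The conclusion assumes that the adjusted model is reasonably specified and that the actual loss is close to the 5 planned. A much larger or strongly one-sided loss would reopen the question.

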### *Measurements*

At the baseline and follow-up clinic visits, participants completed questionnaires and trained study staff conducted physiological measurements (i.e., anthropometry, blood pressure), phlebotomy, and applied the ZioPatch device. Treatment compliance was assessed by a pill count at the follow-up visit. At intervention days 21, 42 and 80 participants were also emailed unique links to online questionnaires, administered via REDCap [15], which queried compliance and asked the following open-ended question about adverse effects: “Since starting the study,

have you experienced anything out of the ordinary?” Participant blinding was also assessed on intervention day 80, the last day of the study.

The ZioPatch was used to identify premature atrial contractions (PACs). PACs are supraventricular arrhythmias associated with the future risk of AF [16-18] and are considered an intermediate phenotype of the arrhythmia, reflecting the underlying cardiac substrate that facilitates the development of AF [19]. Participants were asked to wear the ZioPatches for 2 weeks after each clinic visit. Information obtained from the ZioPatch devices was processed by the ZEUS algorithm, a comprehensive system that analyzes electrocardiographic data received from the device [20]. We counted as PACs isolated supraventricular ectopic beats, supraventricular ectopic couplet total count, and supraventricular ectopic triplet total count. Total PACs were then divided by number of hours the ZioPatch recorded analyzable data, which yielded PACS per hour.

Participants were asked to fast for 8 hours prior to blood draws. Serum magnesium and glucose were measured using the Roche Cobas 6000 at the University of Minnesota Advanced Research and Diagnostic Laboratory. Blood pressure was measured with the participant sitting, after a 5 minute rest, with a random zero sphygmomanometer (Omron Digital Blood Pressure Monitor HEM-907XL). Three measurements were taken; all three measurements were averaged for use in analyses. Height and weight were measured with participants in light clothing, and shoes removed. Height was measured with a research stadiometer and weight with a scale.

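### Does the adherence summary need a stated denominator because the pill count is taken only at the follow-up visit?

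*SAP*

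**What the plan says.** The SAP (Statistical analysis) opens with the purpose of the study: "The goal of the pilot study was to assess adherence to the Mg supplement". ZioPatch feasibility and preliminary PAC data come after it. The planned analysis of adherence is descriptive and by assigned arm: "Descriptive statistics are provided according to treatment assignment for baseline characteristics, adherence, Mg concentrations and other outcomes". The sentence just before it reads "All analyses were intent-to-treat".

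The protocol (Measurements) gives two sources of adherence data. The first is the pill count: "Treatment compliance was assessed by a pill count at the follow-up visit". The second is remote: "At intervention days 21, 42 and 80 participants were also emailed unique links to online questionnaires", "which queried compliance and asked the following open-ended question about adverse effects". The protocol (Study participants) dates the visit: "Ten weeks after beginning the study intervention, participants took part in a follow-up clinic visit, and a second ZioPatch was applied". Treatment then runs two more weeks, to week 12.

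The SAP's sample-size sentence allows for loss, "assuming 5 participants would not complete follow-up", out of a target of 60. Neither document says which source is the adherence measure, what counts as adherent, over which participants it is summarised, or what happens when a pill count is missing.

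**The concern.** A pill count at a clinic visit exists only for people who come to the visit. People who leave a supplement trial may well have stopped their pills, so attendance is close to the thing being measured. A summary limited to attendees would then be too high. The summary is also unadjusted, so the age-stratum and baseline terms in the change regressions give it no protection.

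The possible consequence is practical. Adherence is the first result this pilot is meant to deliver, and a later trial planned on an inflated figure would expect more pill-taking than it gets. With no denominator and no count of missing participants by arm, a reader could not tell how far off the figure might be. The PAC analysis is not in question.

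**Working it through.** **The plan's own figure.** The 5 non-completers belong to the PAC sample-size calculation. A two-sample t-test at 0.79 SD, 80% power and two-sided 5% needs 26.15 per arm, rounded up to 27. That is 54 completers, and 54 + 5 = 59 against the stated 60. With 55 completers the power is about 82%. The target therefore reproduces. It also shows that the 5 is an allowance for log PAC data, not a forecast of missing pill counts: someone who attends but lacks a second recording would still have a count.

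**Size if only attendees' pill counts were reported.** From the SAP: 60 randomised, with 5 taken as missing. Assumed, because the documents give no rates: mean share of pills taken A = 75 to 95% in attendees and B = 0 to 50% in non-attendees.

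All-randomised mean = (55A + 5B)/60, so overstatement = A − (55A + 5B)/60 = (5/60)(A − B).

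| A (%) | B (%) | All 60 (%) | Overstatement (points) |
|---|---|---|---|
| 75 | 50 | 72.92 | 2.08 |
| 75 | 0 | 68.75 | 6.25 |
| 90 | 25 | 84.58 | 5.42 |
| 95 | 50 | 91.25 | 3.75 |
| 95 | 0 | 87.08 | 7.92 |

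If B = A the overstatement is 0. With 2 missing, the range is (2/60)(25) = 0.8 to (2/60)(95) = 3.2 points. If an assumed arm of 30 has 3 missing, it is (3/30)(25) = 2.5 to (3/30)(95) = 9.5 points. If the 5 split 3:2 and A and B are the same in both arms, the between-arm difference shifts by (1/30)(25) = 0.8 to (1/30)(95) = 3.2 points.

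**What a reader can bound from n alone.** Suppose k of 55 attendees are adherent. Over all 60 the proportion lies between k/60 and (k + 5)/60. For k = 50, the attendee figure is 50/55 = 90.9% and the bounds are 50/60 = 83.3% and 55/60 = 91.7%. For k = 44, it is 44/55 = 80%, with bounds 44/60 = 73.3% and 49/60 = 81.7%. The only inputs are the number with a count and the number randomised, and no imputation rule is needed.

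**The texts side by side.** The SAP sentence says adherence, not pill count, and groups participants by assignment without limiting them to attendees. The protocol has a source that reaches non-attendees three times. An attendee-only summary is thus one possible reading of a silent text, not something the plan prescribes.

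**The case for a change.** The best case for a change is that the omission is real and foreseeable. Adherence is the lead goal, the plan itself expects some loss, and two sources with no stated priority leave the analyst a free choice. The intent-to-treat sentence does not settle it: analysing people as assigned supplies no value for a pill count that was never taken. The bounds are also lopsided, 7.6 points down against 0.8 up in the 50-of-55 example, so the likelier error flatters the result. A few sentences and table rows from data already collected would close the gap.

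The omission and the likely direction stand, the direction on condition that non-attendees took fewer pills. The step from there to a required change does not.

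- The size is mostly assumption. The top of the range needs all five to have taken no pills while attendees averaged 95%.
- Setting that extreme against an assumed SD of 10 points (standard error 10/√55 = 1.35) gives 5.9 standard errors; the mild end with SD 20 gives 2.08/2.70 = 0.8. Neither ratio carries much weight for a descriptive figure with no test or threshold.
- The obvious rule would use a non-attendee's last questionnaire answer and count the silent ones as non-adherent. That mixes a count with self-report, understates adherence for anyone who took pills but missed the visit, and is only one of several conventions.
- A missing-at-random sentence for the change regressions would alter no result, since no PAC bias is alleged.

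A limitation that affects every attendee is the timing: the week-10 count covers 70 of 84 days, and the day-80 questionnaire reaches at most 80 of 84. A denominator rule would not touch that either.

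**Conclusion.** No change to the plan follows. The documents leave open the adherence source, definition, denominator and handling of a missing count. But no stated rule produces a wrong number, and the attendee-only reading is not what the text says. The natural way to fill the gap is to describe each source by arm with its n beside the number randomised. That is sound, and it lets a reader work out the best and worst cases.

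Under the least favourable handling, the overstatement is 2.1 to 7.9 points with 5 of 60 missing and 0.8 to 3.2 points with 2 missing. Both ranges rest on assumed adherence of 75 to 95% in attendees and 0 to 50% in non-attendees, and on reading a planning allowance as missed visits. The true size cannot be derived from these documents and may be zero. The sample size and the PAC comparison are unaffected. This judgement relies on the n being shown with the adherence figure, which is ordinary practice for a descriptive table.

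### Does leaving the form of the robust variance unnamed put the 5% error rate at risk in a trial of about 55 completers?

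*SAP*

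**What the plan says.** All of the relevant text is in the SAP, Statistical analysis. Change in each outcome is regressed on treatment, "adjusting for the randomization stratification factor" (two age groups) and the "baseline value of the outcome with robust variance estimates for confidence intervals and P-values". With the intercept, that is four coefficients. A post-hoc sensitivity model adds sex, making five.

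On size, the target is 60 participants, chosen to give 80% power at two-sided 5% for "a difference in the change in log PACs (follow-up minus baseline) between treatment groups of 0.79 standard deviation units". Losses are allowed for by "assuming 5 participants would not complete follow-up". The protocol, Study participants, gives the allocation: "participants were randomized 1:1 to either 400 mg magnesium oxide or placebo". On subgroups: "Pre-specified subgroup analyses were also performed, stratified by baseline magnesium concentration", split at the median.

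The significance threshold is two-sided 0.05 and the software is R 3.4.0. Neither document says which robust estimator is meant, whether it carries a small-sample correction, whether critical values come from the normal or the t distribution, or which R function is called.

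**The concern.** The basic sandwich estimator (HC0) is justified for large samples. In small ones it uses residuals that the fit has already shrunk, so the standard error comes out too low on average. Normal critical values in place of t add to the shortfall. With 55 people and four coefficients the effect should be visible, and with 27 it should be clear.

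If the SAP's wording means HC0, confidence intervals are too narrow and the stated 5% is exceeded. The excess would be largest in the magnesium subgroups, where a chance result could be carried into the design of a later trial. Stating a corrected form would take one sentence, so the omission looks easy to fault.

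**Working it through.** **Inputs.** From the SAP: target 60, 5 losses, effect 0.79 SD, 80% power, two-sided 5%, four coefficients. From the protocol: 1:1 allocation. Derived: 60 − 5 = 55 completers; 55 / 2 ≈ 27 per magnesium subgroup (not stated in the SAP). Residual degrees of freedom: 55 − 4 = 51 and 27 − 4 = 23.

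**The plan's own figure.** Normal formula: n per arm = 2(1.960 + 0.842)² / 0.79² = 15.70 / 0.624 = 25.2, so 26 per arm. The exact two-sample t-test needs 27 per arm, so 54, or 59 with 5 losses. Power with 27 and 28 completers is 82.0%. The stated 60 is reproduced to within one participant.

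**Error rates under each reading.** Null trials were simulated, 40,000 per scenario, with treatment, a binary age stratum (assumed 50/50) and baseline value in the model. Monte Carlo error is about 0.1 to 0.15 points. HC1 rescales HC0 by n/(n − 4); HC2 and HC3 correct each residual for its leverage. Rejection rates (%) at nominal 5%, normal errors:

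| Estimator | n=55, normal ref. | n=55, t ref. | n=27, normal ref. | n=27, t ref. |
|---|---|---|---|---|
| HC0 | 6.5 | 5.8 | 8.9 | 7.3 |
| HC1 | 5.5 | 5.0 | 6.7 | 5.4 |
| HC2 | 5.5 | 4.9 | 6.6 | 5.3 |
| HC3 | 4.6 | 4.1 | 4.7 | 3.7 |

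**Other error shapes** (heavy-tailed, skewed, variance depending on baseline, variance differing by arm). Including the normal case, HC0 spans 5.6% to 6.9% at 55 and 6.8% to 9.5% at 27 over both references. HC2 with t spans 4.7% to 5.4% and 4.6% to 5.9%. HC3 spans 3.9% to 5.1% and 3.0% to 5.2% over both references.

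**Second simulation.** A run with 20,000 replicates, a 40% age stratum and baseline correlation 0.7 agrees: HC0 with normal reference 6.4% to 6.7% and 8.4% to 9.1%; HC2 with t 4.9% to 5.0% and 5.1% to 5.4%.

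**Hand check on the standard errors.** HC0 equals HC1 times √((n − 4)/n): √(51/55) = 0.963 and √(23/27) = 0.923. The mean HC1 standard error over the true SD was 0.994 and 0.977, which implies 0.957 and 0.90 for HC0; the simulation gave 0.957 and 0.901.

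**Interval width, worst reading.** HC0 with normal reference against the model-based t interval (ratios to true SD 0.996 and 0.985; t critical values 2.008 and 2.069):
- n=55: (0.957 × 1.960) / (0.996 × 2.008) = 0.94, about 6% narrower.
- n=27: (0.901 × 1.960) / (0.985 × 2.069) = 0.87, about 13% narrower.

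**Reading the table against the text.** The SAP's sentence fits all eight combinations. At 55 they run from 4.1% to 6.5%; at 27, from 3.7% to 8.9%. Inflation beyond about half a point at 55 needs HC0. With t critical values, every corrected form is within half a point of 5% at 27, or conservative.

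**The case for a change.** The strongest reply is that the silence is itself the fault. At 27, six of the eight combinations exceed 5%. A correction alone does not settle it, since HC1 and HC2 with normal critical values still give 6.7% and 6.6%. The five-coefficient model with sex raises HC0 to as much as 7.1% at 55 and 9.9% at 27. A reader cannot tell whether a subgroup p-value of 0.04 came from a test with a true size near 4% or near 9%, and an open choice could in principle be made after seeing results.

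Much of this stands. The mechanism is real, and error control in the subgroups cannot be verified from the documents. Three points keep it from becoming a required change.

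- Two of the six exceedances, HC1 and HC2 with t, are 0.4 and 0.3 points. The large ones need HC0, which the SAP does not name.
- The corrected estimators are forms of the stated method, so an analyst who uses one follows the plan as written. HC1 or HC2 with t and HC3 are all defensible, and choosing among them is partly preference.
- In the subgroups, multiplicity weighs at least as much. Two independent tests at an exact 5% already give 1 − 0.95² = 9.75% for at least one false positive. With HC0 and normal critical values this is 1 − 0.911² = 17.0%, and with HC2 and t it is 1 − 0.947² = 10.3%. Correcting the variance removes the avoidable part but does not make a lone subgroup result dependable. The documents give no progression rule that rests on one.

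**Conclusion.** The concern does not hold as an error in the plan. The SAP leaves the form of the robust variance open; it does not prescribe an uncorrected one, and the direction of any departure from 5% depends on a choice that the documents do not state. In the main model the least favourable reading costs 1.5 points with normal errors (6.5 − 5.0) and at most 1.9 with unequal arm variances. Corrected forms with t critical values give 4.1% to 5.0%. In the subgroups the least favourable reading costs 3.9 points (8.9 − 5.0), up to 4.5 with unequal arm variances, against 3.7% to 5.4% for the corrected forms with t.

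These figures rest on an assumed age split, assumed error distributions, 5 losses in total, and subgroups of about 27. Given the SAP's stated aims of adherence, device feasibility and preliminary rhythm data, this is missing detail that sound practice fills. The SAP describes the analyses as already done, so what remains is for the report to name the estimator and reference distribution. Until it does, subgroup p-values just under 0.05 should be read with reserve.

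### The magnesium subgroup analysis stratifies at the median but plans no estimate of how the treatment effect differs between the two halves

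*SAP*

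**What the plan says.** The SAP (Statistical analysis) gives the subgroup analysis one sentence: "Pre-specified subgroup analyses were also performed, stratified by baseline magnesium concentration", below the median against at or above it. It does not write out the subgroup model or say which outcomes are covered.

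The main model is described as follows: "Linear regression was used to evaluate whether change in outcomes differed according to treatment assignment". It adjusts for age stratum and the "baseline value of the outcome with robust variance estimates for confidence intervals and P-values". Sex is added only in a post hoc sensitivity analysis. For PACs, "we pre-specified using log PAC burden for analysis and reported the ratio of geometric means". The one inferential rule is a two-sided p-value below 0.05, which "was used to indicate statistical significance"; subgroup results have no rule of their own.

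No product term, heterogeneity test or between-half difference appears in the SAP or the protocol. The SAP makes no claim of effect modification. Its stated aims are adherence, ZioPatch feasibility and to "collect preliminary data on PACs, a predictor of AF".

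**The concern.** The usual reason to split participants at a median is to ask whether the treatment effect differs between the parts. Two stratum-specific analyses answer a different question: what the effect is in each half. The difference between them needs its own estimate and standard error.

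Without that estimate, a reader is likely to compare the two P-values. Each half holds about a quarter of the completers per arm, so power within a half is low and chance alone will often put one half below 0.05 and the other above it, even when the true effect is the same in both. A misread subgroup result could then colour how the pilot's PAC data are used later. That last step is an inference, not something the documents state.

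**Working it through.** **Inputs from the documents.** SAP: target 60, difference 0.79 SD in change in log PACs, 80% power, two-sided 5%, 5 non-completers, hence 60 − 5 = 55 completers. Protocol, Study participants: 1:1 allocation, "using block randomization within two strata of age" only, so magnesium is not a stratum.

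**Assumptions.** Outcome SD = 1; log PACs as the outcome; an even median split (27 and 28); arms of 13 and 14 in one half and 14 and 14 in the other. Effect sizes other than 0.79 SD, and all variance reductions, are assumed because the documents give none.

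**The plan's own figure.** A two-sample t-test at 0.79 SD needs 27 per arm: 54 + 5 = 59, which agrees with 60. The normal approximation gives 26 per arm: 52 + 5 = 57. Power with 55 completers is 0.82 by the t-test.

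**Power within each half.** Noncentral t, df = n1 + n2 − 2, noncentrality d / √(1/n1 + 1/n2). The chance that exactly one half is significant is p1(1 − p2) + p2(1 − p1).

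| Common effect (SD) | Power, 13 vs 14 | Power, 14 vs 14 | Exactly one significant |
|---|---|---|---|
| 0 | 0.050 | 0.050 | 0.095 |
| 0.2 | 0.079 | 0.080 | 0.147 |
| 0.5 | 0.239 | 0.247 | 0.368 |
| 0.79 | 0.505 | 0.521 | 0.500 |
| 1.2 | 0.849 | 0.863 | 0.246 |

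At 0.79 SD: 0.505 × 0.479 + 0.521 × 0.495 = 0.242 + 0.258 = 0.500. This is the ceiling of 2p(1 − p).

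**Effect of baseline adjustment.** If adjustment removes a fraction r of the variance, d becomes d/√(1 − r).

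| Common effect (SD) | r = 25% | r = 50% |
|---|---|---|
| 0.2 | 0.163 | 0.196 |
| 0.5 | 0.426 | 0.490 |
| 0.79 | 0.465 | 0.315 |
| 1.2 | 0.118 | 0.021 |

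**Chance arm imbalance within halves.** Treating the number on active treatment in the 27-person half as hypergeometric (55 completers, 28 treated) and averaging gives 0.146, 0.364, 0.500 and 0.255 at 0.2, 0.5, 0.79 and 1.2 SD, unadjusted. This changes little.

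**Precision of the missing contrast.** SE = √(1/13 + 3/14) = √(0.0769 + 0.2143) = 0.540 SD. With six coefficients, df = 55 − 6 = 49 and t = 2.01, so the 95% CI half-width is 2.01 × 0.540 ≈ 1.08 SD. Power for a 0.79 SD difference between halves is 0.300. With 25% or 50% of variance removed, the SE is 0.467 or 0.382, the half-width 0.94 or 0.77 SD, and the power 0.381 or 0.528. Averaging over chance imbalance gives SE 0.545, half-width 1.10 and power 0.296.

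**Behaviour of the one-model interaction.** Simulation with n = 55, 20,000 replicates per scenario, covariates unrelated to outcome and a common effect from 0 to 1.2 SD gave a false-positive rate of 0.047–0.053 with model-based variance and 0.070–0.076 with HC0 and a normal reference. The mean absolute gap between the one-model interaction and the difference of separately fitted estimates was 0.08 SD (correlation 0.98).

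**The case against.** - **The contrast can be derived.** The halves contain different people, so if both estimates are reported with CIs, a reader can subtract them and obtain an approximate SE. This is true, and the result would lie close to the one-model interaction. But the plan specifies neither the subtraction nor the reporting it depends on.
- **The argument is from silence.** The SAP is a short summary in the past tense, and an interaction may have been fitted without being mentioned. This stands as a limit: the finding concerns what is described, not everything that was done.
- **The harm is conditional.** It needs P-values in each half and someone who reads discordant results as effect modification. The documents contain neither, and a purely descriptive purpose for the split is possible. This stands, and it is a reason to rate the point low.
- **The size depends on assumptions.** Discordance ranges from 2% to 50%; the 50% is a mathematical ceiling reached at a difference chosen for power, not an expected effect. The calculations use ordinary t-tests, whereas the plan uses adjusted models "with robust variance estimates for confidence intervals and P-values", so they approximate the planned analysis. This stands too.
- **The remedy is underpowered.** About 202 completers would be needed for 80% power at 0.79 SD, against 55. That is correct, but a wide interval tells the reader the question is open, while two discordant P-values can suggest it is settled.

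**Conclusion.** The concern holds. The documents describe stratified analyses only and no estimate of the between-half difference, so the plan as written does not address whether the effect varies with magnesium status. That conclusion rests on the text and not on any calculated figure.

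The size is conditional. If each half is tested at 0.05, discordant significance under a common effect is frequent at moderate effects, and infrequent at large effects once adjustment removes much of the variance. It assumes 55 completers, an even split and log PACs as the outcome.

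Importance is modest. The pilot's stated goals are unaffected, so this is an improvement to consider and not a defect that undermines the trial.

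**What to change.** Keep the stratified estimates with 95% CIs, presented as description. For each outcome analysed by subgroup, add one model in all participants: change in the outcome on treatment, magnesium group (below vs at or above the median), treatment × magnesium group, age stratum and baseline outcome, with robust variance as already planned. Report the interaction with its 95% CI; for PACs this is a ratio of geometric-mean ratios. Base any statement about effect modification on that interval, not on the within-half P-values.

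The cost is one extra model per subgroup outcome on data already collected. The drawbacks are:

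- The analyses are already reported as done, so the contrast cannot be pre-specified and must be labelled exploratory and post hoc.
- It will usually be inconclusive at this sample size.
- It assumes common age and baseline slopes in the two halves, so it need not equal the difference between the separately fitted estimates.
- The SAP does not name its robust estimator. It should be stated, because the simplest choice (HC0 with a normal reference) gives a false-positive rate of about 7–8% for the interaction at this size.
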